### 3.5.6 *Dual-energy X-ray Absorptiometry (DXA) Assessment*

Summary statistics for DXA values and the CFB will be presented by treatment group at each scheduled visit.

### 3.5.7 *Spirometry*

All spirometry results will be presented in data listings.

### 3.5.8 *Other Safety Assessments*

All other safety assessments (echocardiograms, oculofacial assessments and C-SSRS will be presented in patient-level data listings.

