9.4.2. Safety Analyses

All safety analyses will be made on the Safety Population. Safety data will be summarized in tables and listings.

Adverse events will be coded using the Medical Dictionary for Regulatory Activities (MedDRA). Incidence rates for treatment-emergent adverse events (TEAEs), will be summarized

overall, by maximum severity, and by relationship to EDG-5506. Serious adverse events will also be summarized.

The change from baseline in the following safety endpoints will be summarized at each scheduled assessment time point using descriptive statistics:

- Safety laboratory parameters
- Vital signs
- Physical and neurological examination
- ECG parameters
- LVEF as assessed by cardiac echogram
- Pulmonary function as assessed by FEV₁, FVC
- C-SSRS

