### 2.2 Study Objectives and Endpoints

Primary Objective	Primary Endpoints

To assess the safety and tolerability of EDG-5506 in adults with BMD

	

Incidence, frequency and severity of adverse events (AEs), and serious adverse events (SAEs) in participants treated with EDG-5506

Secondary Objectives	Secondary Endpoints

To assess the change in individual safety parameters

	

Incidence of treatment-emergent (TE) abnormal laboratory test results (clinical chemistry, hematology, coagulation and urinalysis)

Change from baseline (CFB) in:

Safety laboratory parameters

Vital signs

Physical and neurological examinations

Cardiac function, as assessed by electrocardiogram (ECG) parameters

Cardiac function, as assessed by an echocardiogram

Pulmonary function, as assessed

	

by forced expiratory volume in one second (FEV1) and forced vital capacity (FVC)

○ Columbia Suicide Severity Rating Scale (C-SSRS)

• To assess the PK profile of EDG-5506 in adults with BMD

	

• PK concentration levels of EDG-5506

Tertiary/Exploratory Objectives	Tertiary/Exploratory Endpoints

• To investigate the effects of EDG-5506 on biomarkers of muscle fiber damage in adults with BMD

	

• CFB in biomarker measures as assessed by:

○ Serum creatine kinase (CK)

○ Serum cardiac troponin I

○ Serum myoglobin

○ Serum cardiac troponin T

○ Serum N-terminal prohormone brain natriuretic peptide (NT-proBNP)

○ Plasma troponin I tissue-specific isoforms (fast-skeletal, slow-skeletal)

○ Plasma Somascan® proteomics

• To assess the effects of EDG-5506 on functional measures in adults with BMD

	

• CFB in functional assessments, as measured by:

○ NSAA

○ NSAD

○ 4-stair climb

○ 100-meter timed test

○ Muscle strength testing

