### *3.5.2 Physical and Neurological Examinations*

All physical and neurological examination results will be presented in data listings.

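### LVEF and FVC are change-from-baseline secondary endpoints that the SAP only lists, and treatment-emergent laboratory abnormalities get no participant-level count

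*SAP*

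**What the plan says.** Protocol 9.4.2 sets the rule for safety measures: "The change from baseline in the following safety endpoints will be summarized at each scheduled assessment time point using descriptive statistics". Seven items follow: laboratory parameters, vital signs, physical and neurological examination, ECG, "LVEF as assessed by cardiac echogram", FEV1 and FVC, and C-SSRS. SAP 2.2 keeps all seven as change-from-baseline secondary endpoints, the cardiac one worded as "Cardiac function, as assessed by an echocardiogram".

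The analysis sections of the SAP then differ by item. Laboratory data, vital signs and ECG receive descriptive statistics with change from baseline (SAP 3.5.3 to 3.5.5). For the other four:

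- Examinations (SAP 3.5.2): "All physical and neurological examination results will be presented in data listings".
- Spirometry (SAP 3.5.7): "All spirometry results will be presented in data listings".
- Echocardiogram and C-SSRS (SAP 3.5.8): "All other safety assessments (echocardiograms, oculofacial assessments and C-SSRS will be presented in patient-level data listings".

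DXA is named as an endpoint in neither document, yet SAP 3.5.6 says: "Summary statistics for DXA values and the CFB will be presented by treatment group at each scheduled visit".

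SAP 2.2 also has the secondary endpoint "Incidence of treatment-emergent (TE) abnormal laboratory test results (clinical chemistry, hematology, coagulation and urinalysis". For laboratory abnormality, SAP 3.5.3 tabulates four result categories (normal, the two grades of abnormal, not done) at each visit, gives absolute and percentage change, and lists the values.

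**The concern.** A named endpoint should have an analysis that delivers it. For LVEF and FVC the SAP names a change from baseline but plans no summary of that change.

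These measures matter here. Protocol 2.2.1 describes a disease that wastes both skeletal and cardiac muscle, and Protocol 5.2 excludes people with an ejection fraction below 45% or FVC predicted below 65%. Safety is the primary objective. As the SAP stands, the course of cardiac and pulmonary function over up to 24 months would reach the clinical study report only as rows in a listing.

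The laboratory endpoint has a different gap. Incidence means the number of participants with at least one new or worse abnormality. SAP 3.1.8 defines treatment emergence for adverse events only, and no section counts participants across visits.

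**Working it through.** The plan gives no figure to reproduce: no hypothesis test is planned and the sample size is empirical (Protocol 9.1, 9.2). The check is a comparison of text, with counts from the Schedule of Activities.

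**1. Items in Protocol 9.4.2 against the SAP**

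| Item | SAP 2.2 | SAP analysis | Table in SAP Appendix A |
|---|---|---|---|
| Laboratory | change endpoint | summary (3.5.3) | 14.3.4.1 to 14.3.4.4 |
| Vital signs | change endpoint | summary (3.5.4) | 14.3.3 |
| ECG | change endpoint | summary (3.5.5) | 14.3.5 |
| Examinations | change endpoint | listing (3.5.2) | none |
| LVEF / echocardiogram | change endpoint | listing (3.5.8) | none |
| FEV1, FVC | change endpoint | listing (3.5.7) | none |
| C-SSRS | change endpoint | listing (3.5.8) | none |
| DXA (not in 9.4.2) | not an endpoint | summary (3.5.6) | 14.3.6 |

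Three of seven are summarised and 7 − 3 = 4 are listed only. Two of those four, LVEF and FVC, are clearly numeric. FEV1 is named with FVC in both endpoint lists, but Protocol 8.2.7 mentions recording only FVC and FVC% predicted. Appendix A also names no listing for C-SSRS.

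**2. Numeric assessments left without a summary**

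Marks are counted along each row of the schedule, with the first taken as baseline. Column alignment is unreliable in the text supplied, so only row totals are used.

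- To Month 12: echocardiogram 3 − 1 = 2; spirometry 7 − 1 = 6; together 8. DXA 2 − 1 = 1.
- To Month 24: add echocardiogram 1, spirometry 2, DXA 1. This gives echocardiogram 3, spirometry 8, together 11; DXA 2.
- For eight participants (Protocol 9.2): 8 × 8 = 64 to 8 × 11 = 88.

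DXA, with 1 to 2 post-baseline assessments each, is summarised. LVEF and FVC, with 8 to 11 between them, are not.

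**3. Laboratory incidence from by-visit tables**

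Hematology and chemistry have 9 + 4 = 13 scheduled post-baseline visits to Month 24. Suppose eight participants, with one abnormal result at each of eight visits. If it is always the same person, incidence is 1/8 (exact 95% interval 0.3% to 52.7%). If it is a different person each time, incidence is 8/8 (63.1% to 100%). The by-visit table is identical in both cases, so it does not determine the endpoint. SAP 3.5.5 shows the missing form: it gives the number and percentage of subjects in each QTc category.

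**4. Precision of the missing summaries**

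The 95% half-width for a mean change with n = 8 is t(0.975, 7) / √8 = 2.365 / 2.828 = 0.836, or about ±0.84 SD.

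**The case against.** **A difference is allowed.** SAP 1 says the SAP supersedes the protocol's statistical section. But the same sentence promises that substantial differences will be identified, and SAP 5 declares none. That declaration is made against Amendment 4, whose Section 9.4.2 was not supplied, so a deviation from that version cannot be shown and is not claimed. The mismatch with the supplied protocol stands, as does the one between SAP 2.2 and SAP 3.5, which depends on no protocol version.

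**General rules cover it.** SAP 3.1.5 says continuous data are generally summarised, and table shells are separate documents. The assessment-specific sections say listings and Appendix A has no tables, so the specific text governs.

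**Little is lost in about eight people.** This largely stands. SAP 6 lists all data, echocardiograms are read at the site for safety, and an independent committee reviews the data. Clinically significant laboratory and examination findings become adverse events (Protocol 8.2.1, 8.2.3) and are counted per participant (SAP 3.5.1.2). But small numbers did not prevent tables for vital signs, ECG or DXA, and the adverse event route does not give change in LVEF or FVC. It also misses laboratory abnormalities judged not clinically significant or attributed to the disease. SAP 3.5.3 does tabulate the former, but only by visit.

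**Four of seven overstates it.** C-SSRS and examinations have no obvious numeric change. That is fair: the firm loss is two of seven.

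**Eight is the evaluable target, not the Safety Population.** This also stands. Protocol 2.3.1 reports 12 adults with BMD dosed by May 2022. If 12 entered this study (an assumption), the counts become 12 × 8 = 96 to 12 × 11 = 132, and the half-width 2.201 / 3.464 = 0.64 SD. Withdrawal or rollover before Month 24 lowers the counts, and re-enrolment could raise them. They show scale, not harm.

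**Conclusion.** The concern holds and should be fixed before database lock. The SAP names change in cardiac and pulmonary function as secondary endpoints and provides no summary of either, although the supplied protocol plans one at each scheduled time point. It also names a laboratory incidence endpoint that its by-visit tables cannot yield.

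The size is four of seven planned summaries replaced by listings, two of them clearly numeric. That is 8 to 11 numeric assessments per participant, assuming one pass through the schedule and follow-up to Month 12 or Month 24. SAP 3.3.1 counts early rollover as completion, so many participants may fall short of 11.

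The consequence is confined to descriptive reporting. No test, error rate or sample size is affected, and the individual data remain available.

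**What to change.** Before database lock:

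1. Add tables of observed value and change from baseline by visit for LVEF and for FVC, including FVC% predicted, and for FEV1 if it was recorded. Keep the listings beside them.
2. For C-SSRS and examinations, add a simple categorical table of baseline against post-baseline, using the Day 1 C-SSRS as baseline if it was done before dosing. Alternatively, state in SAP 5 that these two are listed only and align SAP 2.2. The categorical table is one option; the protocol does not specify its form.
3. Define a treatment-emergent laboratory abnormality, for example normal at baseline and abnormal afterwards, or a worse category than at baseline. Count participants with at least one, using scheduled and unscheduled values. Read this beside the numeric change tables, because category shifts are insensitive for analytes that the disease already raises, such as ALT and AST (Protocol 7).
4. Update SAP 5 against the current protocol version.

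The cost is SAP wording, one definition and a few descriptive tables. No visit or procedure is added. The new summaries will be imprecise, and the laboratory count will partly overlap the adverse event tables.

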## 3.6 Pharmacokinetics (PK)

Samples will be collected for measurement concentrations of EDG-5506 and its metabolites. Summary statistics of concentration values and associated listings will be provided.

## 3.7 Biomarkers

Biomarker samples will be used for analysis of fast and slow skeletal troponin I, cardiac troponin I, cardiac troponin T, NT-proBNP, myoglobin and CK. Summary statistics of these values and associated listings will be provided.

### 3.8 Interim Analysis

No formal interim analysis is planned.

## 4 DATA MONITORING COMMITTEE (DMC)

An independent Data Monitoring Committee (DMC) will be established to enhance the safety of trial participants by providing an independent review of the study data. Details related to the DMC responsibilities, authorities and procedures will be documented in the DMC Charter.

## 5 CHANGES FROM PROTOCOL-SPECIFIED STATISTICAL ANALYSES

This SAP does not deviate from the statistical analysis described in Amendment 4, Version 5 of the study protocol. Any deviations from the protocol or SAP will be described in the CSR.

## 6 PROGRAMMING SPECIFICATIONS

Analyses will be performed using SAS® version 9.4 or higher. All available data will be presented in patient-level data listings which will be sorted by patient identification number and visit date as applicable. Detailed programming specifications will be provided in a separate document. TLF shells and specifications will be provided separately as stand-alone documents.

## APPENDIX A: TABLES, LISTINGS AND FIGURES

Table Number	Title	Population
	Subject Data and Study Conduct	
14.1.1	Participant Disposition	SAF
14.1.2	Demographics and Baseline Characteristics	SAF
14.1.3	Medical History	SAF
14.1.4	Concomitant Medications	SAF
14.1.5	Participant Exposure and Treatment Compliance	SAF
	Efficacy and Clinical Outcome Assessments	
14.2.1	NSAA	SAF
14.2.2	NSAD	SAF
14.2.3	Four-Stair Climb	SAF
14.2.4	100-meter Timed Test	SAF
14.2.5	10-m Walk/Run Test	SAF
14.2.6	Rise-From-Supine Test	SAF
14.2.7	Muscle Strength Test	SAF
14.2.8	ACTIVLIM	SAF
14.2.9	PROMIS-57	SAF
	Safety Assessments	
14.3.1	Overview of Adverse Events	SAF
14.3.2.1	Adverse Events by SOC and PT	SAF
14.3.2.2	Adverse Events by Maximum Severity, SOC and PT	SAF
14.3.2.3	Study-drug Related Adverse Events by SOC and PT	SAF
14.3.2.4	Treatment-Emergent Adverse Events Leading to Study	SAF

	Drug Discontinuation by SOC and PT	
14.3.2.5	Adverse Events Leading to Death by SOC and PT	SAF
14.3.3	Summary of Vital Signs	SAF
14.3.4.1	Summary of Clinical Laboratory Assessments: Chemistry	SAF
14.3.4.2	Summary of Clinical Laboratory Assessments: Hematology	SAF
14.3.4.3	Summary of Clinical Laboratory Assessments: Coagulation	SAF
14.3.4.4	Summary of Clinical Laboratory Assessments: Urinalysis	SAF
14.3.5	Summary of ECGs	SAF
14.3.6	Summary of DXA Assessments	SAF
	Pharmacokinetics	
14.4.1.1	Summary of Pharmacokinetics (PK) Concentrations	PK
	Biomarkers	
14.4.2.1	Summary of Biomarkers	PK

Listing Number	Title
	Disposition
16.2.1.2	Protocol Deviations
	Participant Demographics and Characteristics
16.2.4.2	Medical History
16.2.4.3	Concomitant Medications
	Exposure
16.2.5	Study Drug Exposure and Compliance
	Adverse Events

16.2.7.1.1	Adverse Events
16.2.7.1.2	Serious Adverse Events
	Other Safety Assessments
16.2.8.1	Vital Signs
16.2.8.2.1	Clinical Laboratory Assessments: Chemistry
16.2.8.2.2	Clinical Laboratory Assessments: Hematology
16.2.8.2.3	Clinical Laboratory Assessments: Coagulation
16.2.8.2.4	Clinical Laboratory Assessments: Urinalysis
16.2.8.3	ECGs
16.2.8.4	DXA
16.2.8.5	Spirometry
16.2.8.6	Physical and Neurological Examination
16.2.8.8	Echocardiogram
	Pharmacokinetics (PK) and Biomarkers
16.2.9.1.1	PK Concentrations
16.2.9.2.1	Biomarkers
